University of Kansas Medical Center RESEARCH PROTOCOL INVOLVING HUMAN SUBJECTS TEMPLATE WITH GUIDANCE

Version date: 8/11/2015

Principal Investigator: [name].

Study Title: Impact of Rifaximin Therapy on Intestinal Byproducts in Chronic Kidney Disease

Co- Investigator(s): [name], D.O.

[name], M.B., BChir [name]. [name] [name] [name]

(NOTE: not all sections of this template will apply to all projects. "N/A" is an acceptable response.)

I. Purpose, Background and Rationale

A. Aim and Hypotheses

1. Begin with a brief introduction to describe the origin and importance of the study.

Trimethylamine-N-oxide (TMAO) is a circulating organic compound produced by the metabolism of dietary L-carnitine and choline. TMAO was recently identified to directly induce atherosclerosis in rodents and is strongly associated with the incidence of cardiovascular events in humans. The proposed investigation is a prospective pilot study to assess the impact of alterations in the intestinal flora by short-term antibiotic suppression (with Rifaximin) and to measure its effect on serum TMAO levels in patients with advanced-stage (stage IV-V) chronic kidney disease.

2. Clearly state the aim(s) and hypothesis(es), listing them by number if there is more than one.

Hypothesis: Treatment of CKD patients with Rifaximin will suppress the bacterial flora that are responsible for the generation of trimethylamine, a TMAO precursor, and subsequently reduce serum TMAO concentrations.

Primary Aim:

 The primary outcome of interest will be the change in serum TMAO concentrations (post-therapy minus pre-therapy TMAO) following Rifaximin administration for 10 days.

Secondary Aims:

- 1. To measure the change in urine TMAO
- 2. To measure the change in serum endotoxin, IL-6, IL-8, TNF-alpha levels
- 3. To measure the alteration of bowel microbiota
- 4. To assess the above changes in steady state, 2 weeks after completion of therapy

B. Background and Significance

1. Study Significance: what the proposed research is intended to accomplish and the importance of the results

The proposed investigation is a prospective pilot study to assess the impact of alterations in the intestinal flora by short-term antibiotic suppression (with Rifaximin) and to measure its effect on serum TMAO levels in patients with advanced-stage (stage IV-V) chronic kidney disease. Results may lead to future investigations to better understand how alterations in TMAO metabolism may impact cardiovascular outcomes in patients with chronic kidney disease.

2. Describe the facts, events, and thought processes leading to the currently proposed research project.

We previously postulated that TMAO levels would be substantially elevated in patients with CKD, and to test this hypothesis we performed a cross-sectional analysis of serum TMAO concentrations in a cohort of patients with varying levels of CKD and normal healthy controls. In this study, we observed serum TMAO concentrations progressively rise in CKD. We seek to determine if circulating concentrations of TMAO can be reduced by alterations to the gut flora.

3. Literature Review: Summarize any pertinent studies supporting this proposed project. Human studies are preferred; include animal studies only if human data are lacking.

Wang Z., et al. Gut Flora Metabolism of Phosphatidylcholine and Cardiovascular Risk. *Nature* 2011.

- Dietary supplementation of mice with choline, TMAO or betaine promoted upregulation of multiple macrophage scavenger receptors linked to atherosclerosis, and supplementation of mice with choline or TMAO promoted atherosclerosis.
- Suppression of enteric microflora in atherosclerosis-prone mice inhibited dietary choline enhanced atherosclerosis.
- Prognostic value for the risk of CVD was determined in humans by measuring fasting levels of TMAO and determining its association with prevalent vascular events, including peripheral vascular disease, coronary artery disease and myocardial infarction.
- In atherosclerosis prone mice supplementation with choline was shown to increase aortic atherosclerosis when compared to atherosclerosis prone mice on a normal chow diet.

Koeth RA, et al. Intestinal Microbiota Metabolism of L-carnitine, a nutrient in red meat, promotes atherosclerosis. *Nature Medicine* 2013

- They revealed that subjects with elevated L-carnitine, if also found to have elevated TMAO, had increased prevalence of cardiovascular disease and higher incidence of major adverse cardiovascular events (MI, stroke or death).
- In mice they found that chronic supplementation with L-carnitine resulted in alteration of cecal microbial composition, enhanced synthesis of TMAO, and increased atherosclerosis but not when intestinal microbiota were suppressed.

Tang WH, et al. Intestinal Microbial Metabolism of Phosphatidylchline and Cardiovascular Risk. *New England Journal of Medicine* 2014.

- Plasma and urinary levels of TMAO and plasma choline and betaine levels were
 measured by liquid chromatography and online tandem mass spectrometry after
 they administered a phosphatidylcholine challenge in 40 healthy participants.
 There were time dependent increases in serum TMAO levels and its D9 labelled
 isotopologue as well as other choline metabolites after the phosphatydlcholine
 challenge. The levels were also assessed before and after suppression of bowel
 flora by use of oral broad spectrum antibiotics (metronidazole 500 mg BID plus
 Ciprofloxacin 500 mg daily for 1 week) in 6 of the participants. Plasma levels were
 suppressed after administration of antibiotics but returned after withdrawal of
 antibiotics.
- They examined the relationship between fasting serum TMAO level and the incidence of major adverse cardiovascular events (death, MI, or stroke) during 3 years of follow up in 4007 patients who underwent elective coronary angiography. Elevated serum TMAO level predicted increased risk of a major adverse cardiovascular outcome after adjusting for traditional risk factors.

[name], et al. Manuscript currently under consideration

- In order to assess TMAO levels in CKD a cross-sectional study was undertaken in a group of patients with variable degress of chronic kidney disease ranging from normal to ESRD (n=104). We observed a graded rise in serum TMAO that corresponded to increasing CKD severity. The median concentrations in dialysisdependent patients was approximately 30 times higher than in control patients (94.4 μM in ESRD compared to 3.3 μM in Controls, P<0.001).
- In a second cross-sectional investigation we evaluated TMAO levels compared with prevalent coronary artery atherosclerosis in a subset of subjects with chronic kidney disease undergoing coronary angiography (n=220). We noted a significant correlation between serum TMAO and coronary atherosclerosis burden quantified by modified Gensini scoring (r=0.15, P=0.03 by Spearman correlation). After multivariable adjustment for traditional cardiovascular risk factors the correlation remained significant (P=0.048).

C. Rationale

1. Explain how the background information from the literature supports the current proposed hypothesis(es).

It is a known phenomenon that patients diagnosed with chronic kidney disease (CKD) exhibit a high prevalence of cardiovascular disease which largely accounts for the remarkably high mortality in this group. The average 5-year survival for patients receiving chronic dialysis therapy is approximately 35%, with >50% of this mortality resulting directly from cardiovascular causes (1). It is apparent that patients with chronic kidney disease experience an increased burden of atherosclerosis compared to matched individuals with normal kidney function. The presence of traditional risk factors for the development of atherosclerosis, such as diabetes, smoking and hypertension, do not fully account for the accelerated atherosclerosis observed in CKD patients. From this observation it appears that patients with altered renal function possess unique risk factors that contribute to the disease pathophysiology in this setting.

One potential, yet unproven, risk factor for the development of atherosclerosis in patients with chronic kidney disease is trimethylamine-N-oxide (TMAO). TMAO is a circulating organic compound produced by enteric microbial metabolism of dietary L-carnitine and choline (2,3) which results in formation of trimethylamine (TMA), a metabolite that is absorbed from the intestine and subsequently oxidized by hepatic flavin monooxygenase enzymes to form TMAO (6). TMAO has been observed to directly induce atherosclerosis

in rodents and was found to be strongly associated with the incidence of cardiovascular events in humans (2-5). In normal physiologic conditions, circulating TMAO is rapidly removed from circulation primarily by excretion into the urine (7). We previously postulated that TMAO levels would be substantially elevated in patients with CKD, and to test this hypothesis we performed a cross-sectional analysis of serum TMAO concentrations in a cohort of patients with varying levels of CKD and normal healthy controls. In this study, we observed serum TMAO concentrations become markedly elevated in the advanced stages of CKD, with end-stage renal disease (ESRD) patients exhibiting mean levels 30-fold higher than healthy controls.

If TMAO contributes to atherosclerosis formation in CKD patients, therapeutic interventions to reduce TMAO production may represent a method to reduce cardiovascular morbidity and mortality in this population. Prior studies suggest that short-term suppression of gut flora with antibiotics dramatically decreased TMAO levels in patients with normal kidney function (5); however, this approach has not yet been tested in patients with CKD that exhibit much higher serum levels of TMAO.

Rifaximin is a novel antibiotic that is currently approved for treatment of hepatic encephalopathy in patients with end-stage liver disease. Rifaximin demonstrates little systemic absorption, with 97% of the parent drug being excreted unchanged in the feces (9). Its primary use is to target pathogenic intestinal bacteria in various disease states , including cirrhosis and traveler's diarrhea. In this study we seek to evaluate whether Rifaximin will decrease levels of TMAO in patients with advanced kidney disease and to study the effects of Rifaximin on the intestinal microbiome of patients with CKD.

Explain how the performance of this proposed project will advance our knowledge in this field, and/or improve our understanding of the disease or physiological condition being studied.

This study will determine if elevated levels of TMAO in CKD are at least partially dependent on the presence of certain intestinal flora and if serum TMAO levels are modifiable by therapy with Rifaximin.

3. Explain how this study might improve the diagnosis or treatment of the disease being studied (if applicable), or advance knowledge in the field.

This will provide preliminary evidence to support the intestinal flora as a target for reducing TMAO levels in CKD patients.

II. Research Plan and Design

A. Study Objectives: List the broad research goal and specific aims of the project in a clear, concise manner using lay language. List primary and secondary; include statement of purpose. (NOTE: the Department of Biostatistics is available to assist with study design, sample size calculation, and statistical analysis matters. Contact [name] or see Consulting and Collaboration at Department of Biostatistics

Primary objectives: To determine if administration of Rifaximin for the period of 10 days reduces serum TMAO levels.

Secondary Objectives: To determine if Rifaximin additionally alters urine TMAO, serum endotoxin,IL-6, IL-8, TNF-alpha, and the composition of the intestinal flora and the composition of the intestinal flora as compared to placebo.

B. Study Type and Design: Indicate type of study (e.g. cross-sectional vs. longitudinal; multicenter, controlled, cross-over, randomized, chart review, case cohort, non-interventional, etc) and describe how the study is to be conducted to accomplish specific aims of the project.

This is a prospective, randomized, placebo-controlled, double-blinded interventional pilot study.

C. Sample size, statistical methods, and power calculation

1. Describe the analytic and statistical methods to be used, including the method of randomization and randomization ratio (1:1; 3:1; etc) if randomization is used.

We seek to enroll a total of 30 patients for this investigation, 15 participants will receive Rifaximin and 15 control patients will receive placebo with a 1:1 randomization ratio. No prior data are available on the impact of rifaximin on serum TMAO levels in CKD patients; therefore, our sample size determination is based on a conservative estimate of the predicted change in TMAO and the expected response variability between study participants. Based on an expected true mean change in serum TMAO concentrations in matched pairs of -30% with a standard deviation of -30% change, we will need to study 13 subjects to be able to reject the null hypothesis that this response difference is zero with 90% power and type I error probability of 0.05. We plan to enroll 15 subjects in our intervention groupin case the observed variability in this response is greater than our initial prediction.

2. If blinding (masking) is involved, describe the procedures, indicate who has the code to the blind, and the circumstances and procedures for breaking the code.

Blinding will be involved in this study. The primary investigator, study participants, and team members involved in serum/urine end point analyses will be blinded to treatment arm. The investigational pharmacy is responsible for study group assignment and is not blinded. The study team member involved in the fecal bacterial genome analysis will not be blinded, as knowledge of treatment arm will be necessary for the accurate assessment of changes in fecal microbiome composition among study participants.

3. State the maximum number of subjects to be enrolled in each group. Include power calculations to explain what can be studied with the proposed sample size and specify the statistical tests that will be used to test **each** hypothesis. If the research project needs to be pilot tested, state how many subjects will be enrolled in the pilot test and how the procedures for the pilot test will differ from those used in the research protocol.

There will be a total of 30 subjects enrolled; 15 participants will receive Rifaxmin and 15 will receive placebo.

D. Subject Criteria (See Vulnerable Populations appendix, if applicable): Include age range, gender, disease, and stage of treatment. Justify excluding subjects based on race or

gender (including child-bearing potential for women), age (children), or non-English speakers.

- 1. Inclusion criteria: State the criteria for inclusion in the study in a specific and detailed manner.
 - Patients 18 years of age or older
 - Stage IV-V chronic kidney disease (eGFR ≤ 39 ml/min/1.73m²)
- 2. Exclusion criteria: State the criteria for excluding potential subjects from the study in a specific and detailed manner.
 - Patients with normal renal function or those with less advanced kidney disease
 - Inability or unwillingness to provide consent
 - Patients undergoing hemodialysis or peritoneal dialysis therapy or those who have undergone organ transplant
 - Patients who may be pregnant
 - Hemodynamically unstable patients
 - Patients with liver failure, pancreatic insufficiency, or inflammatory bowel disease
 - Patients with ongoing or recent infection and those with history of C-diff infection
 - Patients with abnormal bowel structure secondary to surgical or anatomic variations
 - Patients on certain medications including immunosuppressants, antidiarrheal agents, and current or recent (within the last 2 months) use of antibiotics
- 3. Withdrawal/Termination criteria: Include the specific circumstances in which the subject's participation will be terminated by the investigator. Include any necessary safety precautions to be applied to those who withdraw (tapering drug doses, evaluative x-ray, etc.)
 - Participation may be terminated if subject is found to not meet the inclusion or exclusion criteria. Participants may withdraw at any time.
- 4. Clarify whether a study subject may participate in another research study while participating in this research study.
 - Patients should not participate in another research study while taking the study medication but exceptions may be made dependent on the nature of the other research study.

E. Specific methods and techniques used throughout the study

1. Laboratory tests: Methods for collecting specimens and data. Indicate purpose, amount and timing of tests performed (e.g., blood tests, urine tests, CSF tests, EKGs, etc.). Include specific test components and estimated volume and type of specimens needed for each test.

Serum and urine samples (30ml each) will be collected at the baseline and post-therapy visits (day 0, day 11, and day 25) for measurement of TMAO, endotoxin, IL-6, IL-8, and TNFa levels. Fecal specimens will be collected at these same time points in order to assess changes in the intestinal microbiome after administration of Rifaximin.

2. Study Procedures: Describe each procedure to be used in the study, including the instruments used, time required for each procedure, cognitive assessments, etc.

Blood, urine and stool samples will be collected for analysis. Aside from venipuncture there will be no other procedures.

3. Clearly indicate which procedures, tests, visits, etc., are parts of usual standard therapy and which are performed solely for research purposes. Make it clear which tests are routinely performed for clinical care but are providing data for the research (and are billable to insurance companies), and which tests are only performed for research purposes (not billable to insurance companies).

Any samples collected during the specified research appointments will be used for research purposes only and will not be billed.

4. Describe the fate of any body component (blood, CSF, bone marrow, etc.) used in the study, emphasizing confidentiality of labeling of the sample and the sample's destruction or storage.

Blood, urine and stool samples will be labeled with study information and by the subjects' unique study ID. They will be analyzed in the lab of [name] and the lab of [name] at the University of Pittsburgh Medical Center. Additional serum and urine samples will be stored in a -80°C freezer in [name] lab for those patients consenting for sample storage.

5. Timeline: Consider attaching a study flow chart illustrating subject visits and tests or procedures to be performed at each visit **and/or** include a chart or graph format that reflects the project activities and anticipated time frame of completion.

Day 0 (baseline visit): Consented participants will have an initial appointment dedicated to the collection of baseline samples and study medication will be dispensed at this visit. Complete review of the patient's history and physical examination will be recorded. All study participants will continue receive standard of care treatment for their chronic kidney disease. Study participants will be provided with a 10-day course of Rifaximin. A medical history will be obtained, including current medications, comorbid conditions, lifestyle indicators (such as tobacco and alcohol use), review of recent laboratory studies (such as BMP, CBC, and lipids); this information will be recorded and stored on all study participants. Serum, urine and fecal samples will be collected at this

visit. On Day 1, study participants will begin Rifaximin 550mg PO BID or placebo for a total of ten days duration.

Day 11 (post-therapy follow-up visit): Study participants will provide stool samples within 24 hours of their last dose of Rifaximin or placebo. Serum and urine samples will be drawn at this study visit. Vital signs will be checked and a brief interview will be conducted to assess for any potential adverse reactions to the study medication. Follow up visits can be arranged at the patient's request if needed.

Day 25 (steady state follow-up visit): Study participants will provide stool samples. Serum and urine samples will be drawn at this study visit. Vital signs will be checked and a brief interview will be conducted to assess any recent health changes.

- **F. Risk/benefit assessment:** As appropriate, address the following parameters as each relates to the individual subject in the study. Be sure to include consideration of study assignment (Arm A, Arm B, placebo, active substance, etc):
- 1. Physical risk: Rifaximin has known potential side effects. Since this medication has primarily been studied in patients with advanced liver disease, it is unclear which of these side effects are unique to this population of patients. The most common side effects reported in patients with liver disease included peripheral edema, ascites, nausea, dizziness, fatigue, headache, muscle spasms, pruritus, abdominal pain, and rash. Most common side effects in patients without liver disease are believed to be gastrointestinal in nature; mainly including nausea, abdominal pain/bloating, and diarrhea. Serious reactions have been reported by the manufacturer with this therapy, including superinfection with clostridium difficile, hypersensitivity reaction, angioedema, anaphylaxis, and exfoliative dermatitis. The risks associated with venipuncture in order to obtain blood samples carries a small risk of excessive bleeding, vasovagal syncope, hematoma/infection at the site of vein puncture, and potentially multiple punctures in order to locate veins.
- 2. Psychological risk: No anticipated risk.
- 3. Social risk: No anticipated risk.
- 4. Economic risk: Low anticipated risk. The patient will have no cost associated with the study. In the instance of an adverse event, normal medical treatment should be sought and insurance billed as is standard.
- 5. Potential benefit of participating in the study:
 - a. To the individual subject and/or parent if any: Individuals are not expected to benefit directly from participation in this study.
 - b. To the population from which the subject is drawn: This study may provide critical insight into understanding the altered metabolism of TMAO in CKD and provide preliminary evidence to support the development of future large-scale studies.
 - c. To science, society, and humanity in general: This may lead to development of interventions which could decrease the burden of cardiovascular disease in patients with chronic kidney disease, ultimately reducing health care costs and outcomes for patients with these conditions.
- **G. Location where study will be performed:** Indicate where all portions of the study will take place and where the research subject's records will be kept.

This study will be conducted at the University of Kansas Hospital with patients being recruited from the outpatient nephrology clinics. Records will be kept on secure spreadsheets that can only be accessed by the study team.

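### No stratification and no covariate are specified, so at 15 per arm a chance CKD-stage imbalance could rescale the estimated µM effect by about 11–20% under assumed stage differences (minor)

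*Combined protocol and SAP*

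**What the plan says.** On allocation, II.C.1 gives numbers and a ratio only: "15 participants will receive Rifaximin and 15 control patients will receive placebo with a 1:1 randomization ratio". II.C.2 adds that "The investigational pharmacy is responsible for study group assignment and is not blinded". Neither section describes blocks, strata or how the list is generated.

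Eligibility (II.D.1) pools "Stage IV-V chronic kidney disease" with a single eGFR ceiling of 39 ml/min/1.73m² and no cut-point between the two stages.

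The primary outcome (I.A.2) is the "change in serum TMAO concentrations (post-therapy minus pre-therapy TMAO"), a difference in concentration units. The sample size (II.C.1) is instead framed in percent: "Based on an expected true mean change in serum TMAO concentrations in matched pairs of -30% with a standard deviation of -30% change".

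On the link between stage and TMAO, the investigators' cross-sectional study in I.B.3 (n=104, normal function to ESRD) reports: "We observed a graded rise in serum TMAO that corresponded to increasing CKD severity". Section I.C.1 adds that TMAO is cleared mainly in the urine.

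Section V.A plans one test, a paired two-sided t-test of pre- against post-treatment TMAO. It contains no between-arm comparison and no covariate.

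**The concern.** Kidney function is known before allocation and is the one patient characteristic that the protocol's own data connect to TMAO. With 15 per arm, chance can put noticeably more stage V patients in one arm. Because the outcome is a difference in µM, a 30% fall from a high starting level counts for more than a 30% fall from a low one. The stage mix of the rifaximin arm can therefore change the apparent size of an unchanged drug effect, and with it the chance of reaching significance. Nothing in the analysis as written would adjust for this.

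**Working it through.** **The plan's own figure.** Effect/SD = 30/30 = 1.0. For a paired two-sided t-test at alpha 0.05, noncentral-t power is 88.3% with n=12, 91.1% with n=13 and 94.9% with n=15. The statement "we will need to study 13 subjects" "with 90% power and type I error probability of 0.05" therefore reproduces. It is a within-patient calculation, so balance between arms does not enter it.

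**Inputs for the check.** From the documents: 30 patients, 15 per arm, a 30% fall, SD 30%. Assumed: 15 of 30 patients are stage V; stage V/IV TMAO ratio k = 2 to 4; the same proportional response in both stages; no change on placebo.

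**1. Probability of imbalance.** With x stage V patients in the rifaximin arm, P(x) = C(15,x)² / C(30,15).
- Sum of C(15,x)² for x = 0 to 5: 1 + 225 + 11,025 + 207,025 + 1,863,225 + 9,018,009 = 11,099,510.
- Doubled for both tails and divided by 155,117,520: 22,199,020 / 155,117,520 = 14.3%.
- If only 10 of 30 were stage V, a 7:3 or worse split would have 24.5% probability and 8:2 or worse 5.0%.

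**2. Rescaling in µM.** Take the stage IV mean as 1 and the stage V mean as k. Mean level in an arm with 10 stage V and 5 stage IV, relative to a balanced arm: [(10k + 5)/15] / [(k + 1)/2].
- k=2: 1.667/1.5 = 1.111
- k=3: 2.333/2 = 1.167
- k=4: 3.0/2.5 = 1.200

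A proportional fall scales with the mean level, so the expected µM change moves by +11%, +17% or +20%, and by the same amounts downward for a 5:10 split.

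**3. Effect on a between-arm test of absolute change.** Simulation with k=3, stage IV median 20 µM, between-person log SD 0.5, within-person log SD 0.28 and true effect log(0.7) = −0.357 (concentrations and SDs assumed). The implied SD of log change is 0.28 × √2 = 0.40. If the post/pre ratio is lognormal with mean 0.7 and SD 0.3, the protocol's figures give √ln(1 + (0.3/0.7)²) = 0.41, so the total noise fits the plan. A 10:5 split gives about −16.3 µM with 51% power; a 5:10 split gives about −11.8 µM with 28% power.

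**4. What baseline handling does (same scenario).**
- Post-treatment log TMAO alone would shift by log(3) × (10/15 − 5/15) = 0.366.
- Log ANCOVA on baseline only gives −0.313 or −0.406 (power 55% or 77%). The average residual is about 0.047, so 1 − 0.047/0.366 = 87% of the shift is removed. The remainder arises because one noisy Day 0 value regresses towards its stage mean.
- Log ANCOVA on baseline plus stage gives about −0.36, with power near 65%, in both directions.
- Between-arm log change without stage gives −0.357 and −0.362, power 68% both ways. Percent change gives power 63% and 64%.
- Absolute change with baseline as the only covariate gives −11.3 or −15.9 µM: the shift reverses. Adding stage brings it to −13.5 or −14.0 µM.

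**5. Sensitivity.** Keep the total SD of change but use within-person log SD 0.14, with the rest as differences in response. The baseline-only log residual falls to 0.013–0.018, so 95–96% is removed. Adding stage then lowers average power in the 10:5 and 5:10 splits from about 63% to 60%.

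**6. No drug effect.** With a 10:5 split, absolute, log and percent change all centre on zero and reject 4.4–5.5% of the time. Baseline-only log ANCOVA rejects about 6%.

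**7. Value of adjustment over all allocations.** For absolute change, adding baseline raises power from about 37% to 48% in the scenario of step 3, and from about 45% to 46% when the SD is mostly response heterogeneity. Adding stage to baseline changes average power little.

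**The case against.** The strongest reply is that leaving a 30-patient pilot unstratified is a legitimate choice. Randomisation is valid without it and the standard error covers chance imbalance. That stands: this is an improvement, not an error.

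Second, the only between-group TMAO figures in the protocol (medians 3.3 µM in controls, 94.4 µM in dialysis-dependent patients) do not describe the trial population, because II.D.2 excludes dialysis patients. No stage IV versus stage V value is given, and nothing shows that stage predicts the change on treatment. This also stands: the 30-fold contrast shows a gradient only, and every stage-specific input above is assumed.

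Third, choosing log or percent change removes the problem without using stage. That is correct under the assumptions here, and it is why the log scale is preferred in the fix. It does not dispose of the point, because I.A.2 currently defines a µM difference.

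Fourth, V.A plans only a paired test, in which between-arm balance plays no part. True. But a randomised, placebo-controlled trial needs a between-arm comparison, and its covariates should be fixed when it is written. The missing comparison is a separate and larger gap.

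**Conclusion.** The point holds as a minor one. No stratum or covariate is specified, and with an absolute-change outcome a 10:5 stage split (10:5 or worse: 14.3% if half the patients are stage V) rescales the apparent µM effect by about 11–20% for assumed stage V/IV ratios of 2 to 4.

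Two stronger readings are not supported. A reader might infer that a stage imbalance could pass for a drug effect. Under these assumptions it rescales an effect that exists and does not create one; rejection under no effect stays near 5%, and a baseline table by stage would show the imbalance. A reader might also infer that adjusting for baseline TMAO fails to deal with it. On the log scale it removes about 87% in the case examined, and more if within-person noise is smaller. The residual of about 0.047 is a third of the estimate's SD of 0.14.

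All of this assumes the same proportional response in both stages. Renal clearance makes a stage effect on the change itself plausible, but the documents give no figure for it.

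**What to change.** In V.A, when the rifaximin-versus-placebo comparison is specified, prespecify an ANCOVA, preferably on log TMAO, with baseline TMAO and screening eGFR (or CKD stage) as covariates. Continuous eGFR is preferable, because II.D.1 gives no cut-point between stages IV and V. Both values are already obtained at screening and Day 0, and the covariates can still be prespecified if allocation has begun.

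Optionally, II.C.1 could state that the pharmacy uses permuted blocks within two eGFR strata that together cover all eligible values.

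Cost: one degree of freedom for the extra covariate, and little change in average power from stage itself (slightly lower if the 30% SD is mostly differences in response). If stratified, the pharmacy keeps two lists, and the final split may be 14:16 if a block is incomplete. No extra patients, visits or assays are needed.
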